7. PLANNED ANALYSIS

For End-Of-Text tables, the set of summary statistics is: N / Mean / Standard deviation (StD) / Min / Median / Max.

For tables that are provided for endpoints with some extreme data, median, quartiles and percentiles should be preferred to Mean, StD, Min and Max.

For time-to-event analysis tables the set of statistics is: number of patients [N(%)], number of patients with event [N(%)], <time to event> [days] followed by P25 (25th percentile), median, P75 (75th percentile) and number of patients censored [N(%)]. If not specified otherwise the duration as well as the time to event will be displayed in days.

Tabulations of frequencies for categorical data will include all possible categories and will display the number of observations in a category as well as the percentage (%) relative to the respective treatment group (unless otherwise specified, all patients in the respective patient set whether they have non-missing values or not). Percentages will be rounded to one decimal place. The category 'missing' will be displayed only if there are actually missing values.

7.1 DEMOGRAPHIC AND OTHER BASELINE CHARACTERISTICS

Descriptive statistics are planned for demographic characteristics, disease history, prior therapies, medical history, alcohol and tobacco use, baseline ECOG performance status, and baseline disease assessment.

7.2 CONCOMITANT DISEASES AND MEDICATION

Only descriptive statistics are planned for this section of the report. Concomitant diseases will be coded similarly as adverse events based on the most current Medical Dictionary for Regulatory Activities (MedDRA) version. Concomitant therapies (CTs) will be coded according to World Health Organization (WHO) Drug Dictionary. CTs will be classified according to the Anatomical Therapeutic Chemical (ATC) classification system. The third ATC level will be used to categorize CTs by therapy type. In situations where a medical product may be used for more than one equally important indication, there are often several classification alternatives. As appropriate, patients receiving CTs with more than one possible ATC level 3 category will be counted more than once. Footnotes will clarify this possible double counting in tables.

7.3 TREATMENT COMPLIANCE

Not applicable in this study.

7.4 PRIMARY ENDPOINT(S)

Maximum tolerated dose (MTD) of ezabenlimab (Part I) and ezabenlimab plus BI 754111 combination (Part II);

Number of patients experiencing Dose Limiting Toxicities (DLTs) during the MTD evaluation period in patients with solid tumours

In order to identify the MTD and the recommended dose for ezabenlimab (Part I) and ezabenlimab in combination with BI 754111 (Part II), the number of patients with DLTs at each dose level during Part I and Part II (first three weeks) must be presented. Patients who discontinue during the first treatment course for reasons other than a DLT will be excluded from the determination of the MTD.

The analysis of the MTD is based on a BLRM guided by the escalation with overdose control principle. The MTD is defined as the highest dose for a given schedule that is expected to cause less than 25% risk of the true DLT rate being above or equal to 33% during the MTD evaluation period. Estimation of the MTD during the dose escalation phase of the study will be based upon the estimation of the posterior probability of the incidence of DLT in toxicity categories during the MTD evaluation period for all evaluable patients. The model to be used is specified in CTP Section 7.

In addition, the number of patients with DLTs that occurred during the trial will be summarised at each dose level (Part I and Part II) and each cohort (Part III). The BLRM will be rerun to re-evaluate the MTD and RD together with all relevant data collected during Part III.

Objective response (OR) - confirmed complete response (CR) and partial response (PR) according to RECIST Version 1.1 as assessed by the Investigator

For Part III, OR according to RECIST Version 1.1 will be summarised descriptively with exact 95% Clopper-Pearson CIs. Response data collected after the EOT or the start of subsequent anti-cancer therapy will not be used. This applies to other endpoints based on the response data. Confirmed best overall response (BOR) will be derived according to the following derivation rules:

- If CR or PR: look at subsequent visits, if there is another CR or PR ≥ 28 days and no more than one missing visit (defined by time window [Table 6.7: 1](#)) in between, then the patient has a confirmed response. If there is not another CR or PR ≥ 28 days and / or more than one missing visit between the two responses, then the patient can be a confirmed SD if the CR or PR is ≥ 39 days from start of combination therapy.
- If SD: to be confirmed SD, the measurement must have been taken ≥ 39 days from start of combination therapy (only one reading is necessary).
- Additional details are provided in Table 7.4: 1.

Table 7.4: 1 Details of confirmed BOR derivation rules

Overall response (time point 1)	Overall response (≥ 28 days from time point 1)	Confirmed BOR
CR	CR	CR
CR	PD	SD as long as ≥ 39 days, otherwise, PD
CR	NE/Missing	SD as long as ≥ 39 days, otherwise, NE
PR	CR	PR
PR	PR	PR

Table 7.4:1 Details of confirmed BOR derivation rules (Continued)

Overall response (time point 1)	Overall response (>=28 days from time point 1)	Confirmed BOR
PR	SD	SD as long as >=39 days, otherwise, PD
PR	PD	SD as long as >=39 days, otherwise, PD
PR/SD	NE/Missing	SD as long as >=39 days, otherwise, NE
NE	NE/Missing	NE

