2.1.3 Secondary endpoints

The secondary endpoints of Part I are the following:

[figure not shown]
- The following pharmacokinetics (PK) parameters of BI 754091 will be measured after single administration:
 - C_{max} : maximum measured concentration of BI 754091 in plasma
 - AUC_{0-504} : area under the concentration-time curve of BI 754091 in plasma over the time interval from 0 to 504 hours
- Objective response (OR): confirmed CR or PR according to RECIST v1.1 as assessed by the Investigator.

The secondary endpoints of Part II are the following:

- The following PK parameters of BI 754091 and BI 754111 will be measured after single administration:
 - C_{max} : maximum measured concentration of BI 754091 and BI 754111 in plasma
 - AUC_{0-504} : area under the concentration-time curve of BI 754091 and BI 754111 in plasma over the time interval from 0 to 504 hours
- Objective response (OR): confirmed CR or PR according to RECIST v1.1 as assessed by the Investigator.

The secondary endpoints of Part III are the following:

- Duration of response: defined as the duration from the date of first documented PR or CR according to RECIST Version 1.1 as assessed by the Investigator to the date of progressive disease (PD) or death.
- Disease control: CR, PR, or stable disease (SD) according to RECIST Version 1.1 as assessed by the Investigator.

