5. ASSESSMENTS

5.1 ASSESSMENT OF EFFICACY

5.1.1 Tumour assessments

The tumour response will be evaluated according to RECIST Version 1.1 ([R09-0262](#)) and iRECIST ([R17-0923](#)). The overview of iRECIST will be found in Appendix [10.6](#).

The assessment by the Investigator and/or the local radiologist will be the basis for continuation or discontinuation of the trial in an individual patient (in addition to safety). The baseline imaging must have been performed within 4 weeks prior to treatment with the trial medication and the Investigator will record the target and non-target lesions in the eCRF. The same method of assessment and the same technique must be used to characterise each reported lesion at baseline and during treatment. Lesions in previously irradiated areas may not be used as target lesions. Tumour assessments will be performed at screening (as close as possible to the treatment start and no more than 28 days before the start of study treatment), every 2 cycles (6 weeks \pm 5 days) for the first 6 months, then every 3 cycles (9 weeks \pm 5 days) thereafter, and at the EOT visit (if not performed within the previous 4 weeks).

If a patient discontinues trial medication for a reason other than PD, the tumour assessment according to RECIST and iRECIST will be performed according to standard of care until the last follow-up needed according to the protocol (PD, death, lost to follow-up, end of the trial).

Patients will be allowed to stay on treatment in the case of initial radiological PD, if the Investigator feels that it is in the patient's best interest, and the patient provides an additional consent. If a patient is considered to be confirmed progressive disease according to iRECIST (iCPD), the patient may still continue to receive treatment if the Investigator and sponsor agree that the patient is deriving clinical benefit, and the patient provides an additional consent.

Copies of CT/MRI/PET scan data will be collected by the sponsor for later radiomics assessment. It is planned to explore the potential for enhanced and improved baseline and on-treatment markers/ patterns of early efficacy based on comprehensive quantitative CT metrics, i.e. radiomics features, assessed in standard-of-care medical imaging data.

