7.3.2.2 Secondary endpoint analyses for Part III

Duration of response – for all patients with an OR, the duration of OR will be calculated as follows:

For patients with PD or death:

- Duration of response [days] = date of outcome – date of first assessment indicating OR + 1

For patients without disease progression or death:

- Duration of response (censored) [days] = date of outcome – date of first assessment indicating OR + 1

The censoring rules for OR (i.e., outcome and date of outcome) are described in the TSAP.

The outcome will be assessed according to RECIST 1.1.

Kaplan-Meier estimates will be used to calculate median duration of OR.

Disease control (DC) will be analysed in terms of DC rate (DCR), defined as the proportion of patients with best overall response of CR, PR, or SD according to RECIST 1.1.

Proportions will be presented with 95% two-sided confidence interval using the exact Clopper-Pearson method.

[7.3.5](#)

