7.5.2.2 Other secondary endpoints in Part III

Duration of response according to RECIST Version 1.1 as assessed by the Investigator

Duration of response is defined as the duration from the date of first documented PR or CR according to RECIST Version 1.1 as assessed by the Investigator to the date of PD or death. Duration of response will be summarized descriptively by quartiles with 95% confidence interval (based on the Greenwood's method) calculated from Kaplan-Meier estimate. Kaplan-Meier plots will also be produced. Duration of objective response will use the censoring rule defined in below Table 7.5.2.2:1

[figure not shown]
Table 7.5.2.2:1 Censoring rules and determination of date of event or censoring for duration of response

[figure not shown]
Situation	Outcome (event or censored)	Date of outcome
No other anti-cancer therapy		
Alive and not progressed, no missed radiological assessments window*	Censored	Date of last radiological assessment
Alive and not progressed, one or more consecutively missed radiological assessments window*	Censored	Date of last radiological assessment prior to missed radiological assessments
Progressed, no radiological assessment window* prior to progression	Event	Date of radiological assessment of progression
Progressed, but one or more consecutively missed radiological assessments window* prior to progression	Censored	Date of last radiological assessment prior to missed radiological assessments
Death but no progression, no missed radiological assessment window* prior to death	Event	Date of death
Death without progression, but one or more consecutively missed radiological assessments window* prior to death	Censored	Date of last radiological assessment prior to missed radiological assessments
Initiation of subsequent anti-cancer therapy		
Subsequent anti-cancer therapy started before progression or death, no missed radiological assessments window* prior to start of subsequent anti-cancer therapy	Censored	Date of last radiological assessment before initiation of subsequent anti-cancer therapy

[figure not shown]
* Windows for radiological assessments are defined in [Table 6.7: 1](#)

[figure not shown]
Disease control according to RECIST Version 1.1 as assessed by the Investigator

Disease control is defined as a BOR of CR, PR or SD. Disease control rates will be presented with exact 95% Clopper-Pearson CIs.

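### The end-of-treatment cut in SAP 7.4 is not reconciled with the duration-of-response table, so progression or death after stopping treatment can be lost as an event

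*SAP*

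**What the plan says.** - SAP 7.4, under objective response (OR) for Part III: "Response data collected after the EOT or the start of subsequent anti-cancer therapy will not be used". The next sentence widens the scope: "This applies to other endpoints based on the response data".
- Protocol 2.1.3 defines DoR from first documented response "as assessed by the Investigator to the date of progressive disease (PD) or death". SAP 7.5.2.2 repeats this. Neither sets an end-of-treatment (EOT) limit.
- Protocol 7.3.2.2 leaves the details to the SAP: "The censoring rules for OR (i.e., outcome and date of outcome) are described in the TSAP".
- SAP 7.5.2.2: "Duration of objective response will use the censoring rule defined in below" Table 7.5.2.2:1. The visible rows cover patients alive without progression, progression, death, and new therapy ("Subsequent anti-cancer therapy started before progression or death"). Progression and death count as events unless an imaging window was missed. One row reads "Death without progression, but one or more consecutively missed radiological assessments window* prior to death" and censors at the last scan before the gap. No visible row mentions EOT, and nothing there refers back to 7.4.
- Protocol 5.1.1: if a patient stops for a reason other than progression, tumour assessment "will be performed according to standard of care until the last follow-up" required by the protocol. Protocol 6.2.3.3 follows Part III patients who did not progress on treatment at least every 12 weeks and records the progression date.

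**The concern.** Two SAP rules bear on the same scan. For a responder who stops without progression, 7.4 removes every later assessment, while the table uses them. The SAP does not say which rule comes first.

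If 7.4 is applied as written, stopping treatment, including for toxicity, becomes a censoring reason that appears neither in the DoR definition nor in the visible table. That censoring may be informative. If progression risk is unrelated to stopping, the cut mainly loses events and precision. If progression comes sooner after stopping, the cut lengthens the estimated DoR. It also discards progression dates that the protocol makes sites collect.

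**Working it through.** The plan gives no figure to reproduce here, so the check runs example patients through both rules.

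**Inputs.** Imaging windows from SAP Table 6.7: 1, in days: 1-64, 65-106, 107-148, 149-200, 201-263, 264-326, 327-389, then every 63 days (390-452, 453-515). Formula from protocol 7.3.2.2: DoR = date of outcome − date of first response + 1. The table's first progression row omits the word missed; I read it as no missed window, in line with the rows around it. All examples have first response on day 43 and no new therapy.

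**Progression after EOT.** Partial response on days 43 and 85 (42 days apart, so confirmed under the 28-day rule), EOT day 100, progression scan day 127. Days 43, 85 and 127 fall in three consecutive windows, so none is missed.
- Table: event, 127 − 43 + 1 = 85 days.
- 7.4 first: the day-127 scan is dropped and the patient is censored at day 85, 85 − 43 + 1 = 43 days.

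**Death after EOT.** Same patient, still in response on day 127, death on day 160 (window 149-200).
- Table: event, 160 − 43 + 1 = 118 days.
- 7.4 first, with the death itself still counted: without the day-127 scan, window 107-148 is empty. The missed-window death row applies, and the patient is censored at day 85, or 43 days.
- Not every death is affected. With a last on-treatment scan on day 232, EOT day 240 and death day 255, scan and death share window 201-263. The death is an event at 255 − 43 + 1 = 213 days under both rules, unless 7.4 is read as barring deaths too.

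**Does the text favour one order?** The table restates the new-therapy half of the 7.4 sentence and leaves out the EOT half. SAP 6.6 imputes incomplete start dates of subsequent therapy, expressly for DoR, to no earlier than the day after study medication stops. Protocol 4.2.2.2 requires withdrawal before another anticancer agent is given. New therapy therefore follows the end of treatment. If EOT always cut first, the new-therapy row and its imputation rule would be largely redundant for DoR. This suggests, without stating it, that off-treatment scans were meant to count.

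**Dependence on scan timing.** The examples above assume that the first off-treatment scan keeps the six-week interval. Assumed longer gaps, starting from scheduled scan days, give:

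| Last on-treatment scan | Gap | Progression scan | Result |
|---|---|---|---|
| 127 | 84 | 211 | 149-200 missed; censored under both |
| 169 | 84 | 253 | none missed; rules differ |
| 232 | 84 | 316 | none missed; rules differ |
| 127 | 114 | 241 | 149-200 missed; censored under both |
| 169 | 114 | 283 | 201-263 missed; censored under both |
| 232 | 114 | 346 | 264-326 missed; censored under both |
| 358 | 114 | 472 | 390-452 missed; censored under both at 358 − 43 + 1 = 316 |

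The 84 days are the 12-week follow-up interval; 114 adds the 30 days to the safety visit.

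**Number of patients.** The reference response rates in protocol 7.7.2 (5% to 20%) give 0.05 × 35 = 1.75 to 0.20 × 35 = 7 responders in a cohort of 35. The highest rates assumed there for Cohorts A to D (30% to 45%) give 10.5 to 15.75. Only those who stop without progression and without new therapy are affected, and the documents do not give that number.

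**The case against.** The best defence is that 7.4 selects the data and the table then classifies what remains. With off-treatment scans removed, the patient is alive without progression and is censored at the last scan. For progression this gives one consistent answer. So a reader who infers that progression after EOT has no determinable status goes too far. The SAP does not state this order, however, and the table and SAP 6.6 lean the other way.

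Four other strong readings are tempting, and the documents do not support them.
- *The SAP contradicts the protocol.* Protocol 7.3.2.2 delegates outcome and date of outcome to the SAP, so an extra censoring reason is permitted.
- *EOT could be any of three dates.* The last dose plus 30 days (SAP 6.1) is a safety period and the last administration (SAP 7.7) is an exposure definition; neither uses the term EOT. The protocol defines an EOT visit (6.2.3.1) with imaging unless done within four weeks, which is the natural meaning. One clarifying clause is enough.
- *A stated share of events would be lost, or the median would not be reached.* Such figures depend on assumed scan days, DoR distribution and stopping times. Treatment may also continue beyond one year after case-by-case review.
- *The SAP contains no EOT rule for DoR anywhere.* Text near the table is redacted or not shown, so this can be said only of the visible text.

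It is also fair that DoR is a descriptive secondary endpoint in an exploratory trial without hypothesis tests. That limits the weight of the point but does not remove it.

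**Conclusion.** The concern holds as a conflict between SAP 7.4 and the visible DoR rules in SAP 7.5.2.2. Applied literally, 7.4 turns some progressions after EOT into censored observations that the table would count as events, and through an artificial missed window it can do the same to deaths.

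For one patient the difference can be large: 85 days with an event against 43 days censored, or 118 against 43. Across the trial the size is unknown. It is confined to the DoR event count and Kaplan-Meier quartiles, in the few responders who stop without progression and without new therapy, and it depends on when off-treatment scans take place. OR and disease control are not in question; an on-treatment limit is reasonable there, and protocol 10.6 uses the same limit for best overall response by iRECIST.

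**What to change.** 1. In SAP 7.4, limit the EOT part of the sentence to best overall response, OR and disease control.
2. In SAP 7.5.2.2, state that Table 7.5.2.2:1 governs DoR, using all RECIST 1.1 assessments up to progression, death or new anti-cancer therapy. Progression or death after EOT is then an event, subject to the missed-window rule.
3. State that EOT in 7.4 means the EOT visit and that the scan at that visit is included.

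A sensitivity analysis of DoR with the EOT cut is optional.

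The cost is about three SAP sentences. It needs no new data and leaves the OR rule unchanged. The drawback is that off-treatment imaging follows standard of care and follow-up contact may be by telephone, so scan timing is less regular and many late progressions stay censored under either rule.

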6.2 DETAILS OF TRIAL PROCEDURES AT SELECTED VISITS

The procedures required at each trial visit in all portions of the trial are presented in the [Flow Chart](#) of this protocol. The key procedures required include:

- PK samples throughout the trial
- Reporting of all AEs occurring after the ICF has been signed
- Baseline and on-treatment blood samplings for biomarker and immunogenicity assessments
- Tumour biopsy biomarker assessments
- Tumour assessments (based on CT/positron emission tomography [PET] and/or magnetic resonance imaging [MRI] scan) according to RECIST Version 1.1 and iRECIST must be performed once every 2 cycles (meaning every 6 weeks if there are no delays in cycles but as close as possible to the end of the second of the 2 cycles of treatment if there was a delay) after the start of study medications for the first 6 months, and then every 3 cycles (9 weeks) thereafter.

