6.2.3 Follow up period and trial completion

6.2.3.1 End-of-treatment visit

The EOT visit will be performed as soon as possible but no later than 7 days after permanent discontinuation of the trial medication for any reason or e.g. when the Investigator decided with the patient to permanently discontinue the trial medication or became aware that the trial medication had been terminated.

The assessments of the EOT visit will then be performed instead of at the next planned visit.

If the patient finishes active treatment without having PD, tumour assessment/imaging must be performed at the time of EOT, unless it has been done within the past 4 weeks.

6.2.3.2 30-day safety follow-up visit

The safety follow-up visit is performed 30 (+7) days after the EOT visit. The information collected at this visit must include all new AEs that occurred after the EOT visit, and a follow-up of AEs ongoing at EOT.

A patient will be considered as having completed the trial if he/she discontinues because of PD and has performed the safety follow-up visit 30 days after EOT, or was lost to follow up, or withdrew consent for further evaluation at the EOT visit. If the patient discontinues for any other reason, he/she will be considered as withdrawn.

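### SAP 7.4 discards scans after EOT, so a responder who stops without progression less than about 28 days after the first response cannot be confirmed, and the primary ORR can only fall

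*SAP*

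**What the plan says.** **Exclusion.** SAP 7.4 (Primary endpoints): "Response data collected after the EOT or the start of subsequent anti-cancer therapy will not be used". The SAP extends this to the other endpoints based on response data.

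**Confirmation.** The same section counts a response as confirmed "if there is another CR or PR ≥ 28 days and no more than one missing visit" lies in between. A CR or PR followed by a non-evaluable or missing assessment is scored "SD as long as ≥ 39 days, otherwise, NE" (SAP Table 7.4:1).

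**Scans on treatment.** Protocol 6.2 schedules them "once every 2 cycles (meaning every 6 weeks if there are no delays in cycles") for the first 6 months, then every 3 cycles (9 weeks).

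**Scan at EOT.** Protocol 6.2.3.1, for a patient who finishes treatment without progression: "tumour assessment/imaging must be performed at the time of EOT, unless it has been done within the past 4 weeks". On the visit itself: "The EOT visit will be performed as soon as possible but no later than 7 days after permanent discontinuation".

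**Scans after EOT.** Protocol 5.1.1: "If a patient discontinues trial medication for a reason other than PD, the tumour assessment according to RECIST and iRECIST will be performed", and this "will be performed according to standard of care until the last follow-up needed according to the protocol", that is, until progression, death, loss to follow-up or end of trial.

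**Primary endpoint.** Protocol 2.1.2 and 7.3.1.2 define ORR by confirmed CR or PR under RECIST 1.1. Neither states a cut at EOT.

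**The concern.** The protocol foresees continued RECIST assessment after a stop without progression, and its endpoint does not end at EOT. The SAP discards those assessments when it decides whether a response is confirmed. With the 28-day rule and the 4-week exemption for the EOT scan, this leaves a stretch after each first response in which stopping treatment makes confirmation impossible, whatever later scans show.

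The loss runs in one direction: it can turn a responder into a non-responder but never the reverse. With about 35 patients per cohort, each lost responder costs 1/35 = 2.9 points of ORR. The final criteria are small counts (7, 9 or 14 of 35 in Cohorts D, A and B), so one or two such patients could change how a cohort is read. Disease control is almost unaffected, because SD counts towards it.

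**Working it through.** **Step 1: when confirmation is impossible.** Let t be the days from the first response scan to EOT, for a patient stopping without progression before the next scheduled scan.
- t below about 28: no EOT scan is required, any scan done fails the 28-day rule, and all later scans are excluded. The response cannot be confirmed.
- t of 28 or more: the EOT scan is required and meets the 28-day rule. It can confirm, provided that the EOT in SAP 7.4 means the EOT visit.

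The gap is therefore about 28/42 = 67% of the interval between 6-weekly scans and 28/63 = 44% of the interval between 9-weekly scans.

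**Step 2: an illustration (constructed).** PR on Day 43 and EOT visit on Day 57. The gap is 57 − 43 = 14 days, so no EOT scan is needed and none could confirm. A scan on Day 85 (42 days after the first) still shows PR with no new therapy, but it is after EOT and is not used. The result is SD. NE would need a first response before Day 39; the earliest scheduled scan is Day 43 − 5 = Day 38, so SD is the usual outcome.

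**Step 3: reproduce the plan's figures.** Inputs from protocol Table 7.7.2:1: stage 1 n = 17, total n = 35; interim minimum r1 and final minimum r of 3 and 9 (Cohort A), 4 and 14 (B), 2 and 7 (D). With X1 ~ Bin(17, p) and X2 ~ Bin(18, p):
- P(stop) = P(X1 < r1)
- P(criterion met) = Σ over x ≥ r1 of P(X1 = x) · P(X2 ≥ r − x)

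| Cohort, true ORR | P(stop), computed / printed | P(criterion met), computed / printed |
|---|---|---|
| A, 35% | 3.27% / 3% | 89.75% / 90% |
| B, 45% | 1.84% / 2% | 77.47% / 77% |
| D, 30% | 1.93% / 2% | 92.65% / 93% |

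The printed values are reproduced. Cohort C (closed to recruitment, protocol 3.1) and Cohort E (cancelled, SAP 4) are left out.

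**Step 4: sensitivity.** Let f be the share of true responders lost through the gap. The documents give no value, so f is an assumption. Replace p by p(1 − f); in Cohort A at f = 5%, 0.35 × 0.95 = 0.3325. The expected loss per 35 patients is 35 · p · f.

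| Cohort | f = 2% | f = 5% | f = 10% |
|---|---|---|---|
| A: criterion met | 88.2% | 85.6% | 80.2% |
| A: responders lost per 35 | 0.24 | 0.61 | 1.23 |
| B: criterion met | 74.1% | 68.7% | 58.5% |
| D: criterion met | 91.6% | 89.8% | 86.0% |

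These figures apply the loss at both the interim and the final count. If it is applied to the final count only (full p at the interim, each stage-1 responder then kept with probability 1 − f, and X2 ~ Bin(18, p(1 − f))), f = 10% gives 81.1% (A), 58.7% (B) and 86.5% (D). The difference is under 1 point.

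f is not the rate of early stopping. If 15% of responders stopped without progression before a second 6-weekly scan, at uniformly spread times, f would be at most 15% × 28/42 = 10%.

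**The case against.** **An on-treatment window is a coherent choice.** Protocol 7.3.1.2 is silent on a cut-off, the SAP exists to add detail, and the protocol's exploratory iRECIST best response runs only to end of treatment (Appendix 10.6). The trial is descriptive with no test, and a lower ORR errs on the cautious side. This stands in part: the rule is not wrong in itself. But no visible SAP text labels the primary endpoint as on-treatment, and the protocol's RECIST definition has no such limit. SAP section 4 is partly redacted, so nothing follows about whether the change is declared there.

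**The fix may recover few patients.** Post-EOT imaging has no protocol schedule. Protocol 6.2.3.3 allows follow-up by telephone every 12 weeks, and its list of items contains no response category. In the illustration, a first later scan on Day 57 + 30 + 84 = Day 171 would miss both the Week 12 and Week 18 windows (SAP Table 6.7:1) and fail the missed-visit rule. This stands. A scan up to Day 148 would still qualify.

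**Stronger readings that a reader might infer are not supported.**
- That anyone stopping before a second scheduled scan can never be confirmed: from 28 days on, the required EOT scan can do so. A dose hold for an adverse event (up to 6 weeks, protocol 4.1.4) is not EOT, so scans during it count.
- That the loss is mainly due to immune toxicity: protocol 4.1.4 mandates discontinuation for several toxicities, but no document calls this the main reason for stopping without progression. Protocol 3.3.4.1 lists others.
- That false futility stopping rises: the interim is optional (protocol 7.4), and no visible text applies the SAP 7.4 cut to its count.

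**Conclusion.** The point holds in a limited form. A responder who stops for any non-progression reason, with EOT less than about 28 days after the first response scan, cannot be confirmed and is scored SD, or rarely NE, even if a later scan before new therapy still shows response. Relative to the protocol's own definition the effect on ORR is zero or negative.

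Its size cannot be derived from the documents. At an assumed 2% loss it is small (about 1.5 points off the Cohort A probability, 89.75% to 88.2%). At 10% it is material (about 9.5 points in A, 19 in B, 6.6 in D). These figures treat the table's underlying ORR as including responses that only a post-EOT scan could confirm, and every lost response as recoverable; both make them upper-end for a given f.

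One ambiguity matters. If the EOT means the end of treatment rather than the visit, an EOT-visit scan taken up to 7 days later might also be excluded, and the gap would then cover nearly the whole interval between scans.

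**What to change.** In SAP 7.4:
1. Confirm CR or PR using all RECIST 1.1 assessments up to the earlier of progression or start of subsequent anti-cancer therapy, including those after EOT, with the existing 28-day and missed-visit rules.
2. State that the scan at the EOT visit counts.
3. Keep the on-treatment-only derivation as a sensitivity analysis.
4. Report, by cohort, the number of unconfirmed responders who stopped without progression.

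The cost is a wording change and one reprogrammed derivation, using assessments that protocol 5.1.1 already foresees. The retained new-therapy cut keeps out responses due to later treatment. The downside is that standard-of-care timing will leave some patients without a usable confirmatory scan, so recovery will be partial; item 4 shows how many patients are at issue.
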